Endostapler Hemostasis Study Protocol

September 9, 2019

A proposed study using AEON™ Endostapler Handles and Reloads

(Lexington Medical, Inc., Billerica, Massachusetts)

Principal Investigator:

[name] (surgeon)

Co-Investigator(s):

[name] (surgeon)

[name] (surgeon)

Research Coordinator:

[name]

Primary Outcome Evaluator:

[name]

SUMMARY

The goal of this prospective, multi-center, post-market study is to measure AEON™ Endostapler performance with the EASY/THICK MODE feature for laparoscopic bariatric surgery against the Echelon Flex™ Powered Stapler system from Ethicon. Stapler performance will be evaluated primarily by incidence and degree of staple line bleeding through a third-party blinded primary outcome evaluator. The study will include 60 total consecutive cases of individuals undergoing a planned laparoscopic sleeve gastrectomy (LSG). The LSG procedure will be performed according to institutional standard-of-care and all subjects will undergo standard preoperative evaluation as well as post-operative care. Relevant data will be collected using the Data Collection sheet which should be filled out following each procedure by a member of the surgical or nursing team.

Enrollment: 60 Subjects Meeting Inclusion/Exclusion Criteria

Investigator Masking: None (Open Label)

Primary Outcome Evaluator Masking: Yes (Surgeon and Device)

Devices: AEON™ Endostapler and Echelon Flex™ Powered Stapler System

LEXINGTON MEDICAL AEON™ ENDOSTAPLER BACKGROUND

The AEON™ Endostapler is comprised of a stapler handle and reloads. The handle may accept multiple reloads of single fire cartridges. The AEON™ Endostapler devices were approved by the United States Food and Drug Administration (FDA) under the 510(k) process. Pertinent applications numbers are K171589 and K173443. Devices will be used pursuant to the indications specified in K171589 and K173443, as well as the general guidelines for use of this device on a prescription basis as outlined by the Federal Food, Drug, and Cosmetic Act (1976), and the Code of Federal Regulations Title 21 Part 800-895.

Approved Indications for Use

The AEON™ Endostapler has applications in general, abdominal, gynecologic, pediatric and thoracic surgery for resection, transection and creation of anastomoses.

Available AEON™ Endostapler Reloads

The following two tables contain the available AEON™ Endostapler Reloads, as well as the similar products that they may replace. This is meant as a guide, and the surgeon should read and follow the Instructions for Use and use their own clinical judgment to determine appropriate products to use.

Table 1. Available AEON™ Endostapler Reloads

Reload Type	Cartridge Length	Product Code	Open Staple Height	Closed Staple Height	Minimum Port Size
Gray	45mm	AESR45G	2.0mm	0.75mm	12mm
White	45mm	AESR45W	2.5mm	1.0mm	12mm
White	60mm	AESR60W	2.5mm	1.0mm	12mm
Orange	45mm	AESR45R	3.25mm	1.5mm	12mm
Orange	60mm	AESR60R	3.25mm	1.5mm	12mm
Purple	45mm	AESR45P	4.0mm	1.8mm	12mm
Purple	60mm	AESR60P	4.0mm	1.8mm	12mm
Black	60mm	AESR60B	5.0mm	2.2mm	15mm

Table 2. Approximate Equivalence for AEON™ Endostapler Reloads

AEON™ Endostapler			Echelon Flex™		
Cartridge Color	Open Staple Height (mm)	Closed Staple Height (mm)	Cartridge Color	Open Staple Height (mm)	Closed Staple Height (mm)
Gray	2.0	0.75	Gray	2.0	0.75
White	2.5	1.0	White	2.5	1.0
Orange	3.25	1.5	Blue	3.5	1.5
Purple	4.0	1.8	Gold	3.8	1.8
Purple	4.0	1.8	Green	4.1	2.0
Black	5.0	2.2	Black	4.2	2.3

STUDY DETAILS

Patients will be screened based on the inclusion and exclusion criteria below and will be consecutively evaluated for study enrollment. Each case will be randomly assigned to one of the two FDA approved endoscopic staplers. For the purposes of this study, the surgeons will either use the AEON™ Endostapler or the Echelon Flex™ Powered Stapler system from Ethicon. Enrollment will be contingent on meeting these criteria, and the use of either the AEON™ Endostapler or the Echelon Flex™ Powered Stapler system from Ethicon. Study participation will begin once the subject signs the consent form and will end after the one-month postoperative follow up visit.

Selection of Subjects:

Inclusion Criteria

- Patients undergoing planned laparoscopic sleeve gastrectomy with signed surgery consent form
- Informed consent for study obtained and signed from each subject

Exclusion Criteria

- Planned open surgical approach
- Prior bariatric operation (i.e. revisional bariatric surgery)
- Use of staple line reinforcement material (buttress)
- Patients taking anticoagulants
- Patients under the age of 18 on the date of the surgery

Withdrawal of Subjects:

Subjects are free to withdraw from the study at any time for any reason. Every effort will be made to determine why any subject withdraws from the study prematurely and this information will be recorded in the Clinical Study Report.

In addition, subjects may be withdrawn from the study by the Principal Investigator in consultation with the Sponsor for the following reasons:

- Adverse event
- Protocol violation
- Loss to follow-up

If a subject withdraws prematurely, all data normally collected by study completion should be collected at the time of premature discontinuation or at the scheduled discharge. All subjects who withdraw from the study with an ongoing adverse event must be followed until the event is resolved or deemed stable. At the discretion of the PI, additional follow up visits may be done for subject safety.

Withdrawn subjects will be replaced, until 60 subjects complete the study.

Primary Outcome Measure:

- Incidence of intraoperative staple line bleeding as measured by the provided bleeding severity scale

Secondary Outcome Measures:

- Incidence of postoperative leakage during one-month monitoring period following procedure
- Incidence of reported device-related adverse events
- Incidence of product malfunction during procedure
- Incidence of intraoperative or postoperative blood transfusion within 72 hours of surgery start time
- Postoperative pain level per standard protocol

Steps and Procedures:

The study will include 60 total consecutive cases, randomized for stapler type: 30 with the AEON™ Endostapler and 30 with Echelon Flex™. Surgeries will be performed by either [name], [name], or [name], with at least 5 surgeries of each stapler brand per surgeon.

All patients will undergo the standard preoperative evaluation pathway. Patients must sign informed consent for the operation.

All firings with the AEON™ Endostapler will be done with EASY/THICK MODE for the purposes of this study and shall conform to the AEON™ Instructions For Use (Appendix C). All firings with the Echelon Flex™ should be done according to the Echelon Flex™ Instructions for Use.

In order to measure the primary outcome of incidence and degree of staple line bleeding, a third-party blinded primary outcome evaluator will be used. No sutures, cautery or clips shall be applied to the staple line during stapling, unless required at surgeon's discretion. Following the last firing, a member of the surgical or nursing team or the research coordinator present for the case will count 10 seconds and then capture an image with the laparoscope. The visual should be clear and portray the entire length of the staple line. In the event that bleeding from the staple line requires control prior to the last firing, an additional image should be captured before applying sutures, cautery, clips, etc. These photographs will then be sent by the research coordinator to the primary outcome evaluator either electronically or by mail. The primary outcome evaluator will be blinded to both the surgeon and device of each case. Upon receipt of photographs, the evaluator will evaluate staple line bleeding according to a provided bleeding severity scale and record results in the Bleeding Severity Evaluation Sheet (Appendix B). If a case has more than one image associated with it, the primary outcome evaluator will consider all images when selecting a bleeding severity level.

At the end of each case, the surgical team will fill out the relevant sections of the Data Collection Sheet (Appendix A). Case ID is captured as day/month/year, followed by surgery count for the day – e.g. 071619A for the first surgery performed on July 16, 2019.

All typical post-operative care will continue, including immediate post-operative care prior to hospital discharge as well as the standard one-week and one-month post-operative evaluation. At the end of both the one-week and one-month post-operative period, a member of the surgical or nursing team will fill out the relevant sections of the Data Collection Sheet.

There will be no follow up study data collected after this point, however the patients will continue the standard follow up regimen per the physician's practice.

Surgery Locations:

Surgeries will take place at Southern Surgical Hospital ([name]), Crescent City Surgical Centre ([name]), or Avala Hospital ([name]).

Termination of the Study:

The Principal Investigator reserves the right to terminate the study in the interest of subject welfare. The Sponsor may terminate the study for administrative reasons.

Should the study be terminated, all documentation pertaining to the study must be returned to the Sponsor. Any actions required to assess or maintain study subject safety will continue as required, despite termination of the study by the Sponsor.

Protocol Deviations:

Deviations from the protocol will be assessed as "minor" or "major" in agreement with the Sponsor. Major deviations from the protocol may lead to the exclusion of a subject from data analysis and will be considered on a case-by-case basis.

The Investigator will not deviate from this protocol for any reason without prior written approval from the Sponsor, except in cases of medical emergencies. The Investigator may deviate from the protocol without prior approval only when the change is necessary to eliminate an apparent immediate hazard to a subject. In that event, the Investigator will notify the Sponsor immediately by phone, notify the IRB, and confirm notification to the Sponsor in writing within 5 working days after the change is implemented.

Statistics:

This is an open-label study. Formal sample size calculations were not performed. The number of subjects was chosen based on feasibility and is considered sufficient to meet the study objectives.

Detailed methodology for summary and statistical analyses of the data collected in this study will be documented in the Clinical Study Report.

Direct Access to Source Data/Documents:

The Principal Investigator will ensure that the Sponsor, IRB, and regulatory authorities will have direct access to all study sites, source data/documents, and reports for the purpose of monitoring and auditing. In the event that other study-related monitoring should be done by other parties, those parties will be required to sign a confidentiality agreement prior to any monitoring or auditing.

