Appendix A – Data Collection Sheet

OR Date: _____ Surgeon: _____

Case ID (e.g. 071619A): _____ Hospital: _____

Stapler Type (Circle): AEON™ Endostapler Echelon Flex™ Powered Stapler System

Patient Medications: _____

Patient Gender: _____ Patient Age: _____ Patient BMI: _____

AEON™ Endostapler	Black 60mm	Purple 60mm	Purple 45mm	Orange 60mm	Orange 45mm	Tan 60mm	Tan 45mm
Quantity Reloads Used							

Echelon FLEX™	Black 60mm	Black 45mm	Green 60mm	Green 45mm	Gold 60mm	Gold 45mm	Blue 60mm	Blue 45mm	White 60mm	White 45mm
Quantity Reloads Used										

Intraoperative Outcomes			
Product malfunction (circle)	Yes	No	N/A
Blood transfusion due to staple line bleeding (circle)	Yes	No	N/A

Surgeon overall satisfaction with the stapler used (circle): Dissatisfied Somewhat dissatisfied Neutral Somewhat satisfied Satisfied

Postoperative Outcomes			
Blood transfusion due to staple line bleeding within 72 hours of surgery start time (circle)	Yes	No	N/A
1 Week			
Dysphagia present (circle)	Yes	No	N/A
Nausea present (circle)	Yes	No	N/A
Weight loss:			
Pain level per standard protocol:			
1 Month			
Postoperative leakage during one-month monitoring period following procedure (circle)	Yes	No	N/A
Reported device-related adverse events (circle)	Yes	No	N/A
If yes, please specify:			

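### Pain, the one patient-reported listed outcome, is recorded at one week by staff not required to be masked, on a sheet that shows the stapler brand

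*Combined protocol and SAP*

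**What the plan says.** **Masking.** The Summary gives "Investigator Masking: None (Open Label" and, for the one masked role, "Primary Outcome Evaluator Masking: Yes (Surgeon and Device". The Statistics section repeats: "This is an open-label study". Under Steps and Procedures the masked person's task is limited to photographs: "the evaluator will evaluate staple line bleeding according to a provided bleeding severity scale". Subject masking is not mentioned.

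**Pain.** The last of the five secondary outcomes is "Postoperative pain level per standard protocol". The outcome list names no scale and no time point. Appendix A has a single pain entry, in its 1 Week block, labelled "Pain level per standard protocol".

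**Who records it.** Steps and Procedures says: "At the end of both the one-week and one-month post-operative period, a member of the surgical or nursing team will fill out the relevant sections". Nothing requires that person to be unaware of the device.

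**The form.** In Appendix A the stapler type is circled near the top, followed by reload counts in brand-specific tables. The intraoperative items, the 1 Week items (dysphagia, nausea, weight loss, pain) and the 1 Month items come after these on the same sheet. A free-text line for patient medications sits in the header. The 1 Week block has no analgesic field.

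**The concern.** A pain score is subjective, so it can move if the person giving it or the person writing it down knows which device was used. The plan recognises this risk for bleeding, where it masks the rater to both surgeon and device. It gives no such protection to the one listed outcome that depends on what the patient reports. A recorder who uses Appendix A as laid out has the assignment in view.

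At stake is whether a pain difference between the arms, or its absence, could be attributed to the stapler. Bias of this kind cannot be corrected at the analysis stage. No planned analysis addresses it either, because the Statistics section defers the methods to the Clinical Study Report.

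**Working it through.** The plan gives no figure to reproduce. The Statistics section says that no formal sample size calculation was done, and the documents state no pain SD, alpha, power or target difference. The check has two parts.

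**1. Does any masking reach the pain score?**

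| Step | Section | Masked? |
|---|---|---|
| Stapler used by the surgeon | Summary | No |
| Photographs rated for bleeding | Summary; Steps and Procedures | Yes, to surgeon and device |
| Subject gives the pain score | Not addressed | Not stated |
| Staff enter the one-week score | Steps and Procedures | No requirement |
| Form used for the entry | Appendix A | Shows brand and reload counts |

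The only masked step does not involve pain.

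**2. How large would a bias have to be to matter?** (illustration only)

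From the document: 30 subjects per arm (Steps and Procedures). Assumed, not in the documents: a 0–10 scale, SD of 2 points, two-sided alpha of 0.05, normal approximation.

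- Standard error of the difference: SE = SD × √(2/n) = 2 × √(2/30) = 0.516 points.
- Shift of 0.5 point: 0.5 / 0.516 = 0.97 SE. Shift of 1 point: 1 / 0.516 = 1.94 SE.
- False-positive rate when there is no true difference but a spurious shift b: Φ(b/SE − 1.96) + Φ(−b/SE − 1.96).

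The range in SD units does not depend on the assumed SD. The points column applies SD = 2.

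| Spurious shift (SD) | In points | False-positive rate |
|---|---|---|
| 0 | 0 | 5.0% |
| 0.1 | 0.2 | 6.7% |
| 0.2 | 0.4 | 12.1% |
| 0.25 | 0.5 | 16.2% |
| 0.3 | 0.6 | 21.3% |
| 0.5 | 1.0 | 49.1% |

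For scale, the true difference detectable with 80% power is (1.96 + 0.84) × √(2/30) = 0.72 SD, about 1.4 points at SD = 2. A bias well below that would still distort the test. These figures show sensitivity to a shift. They do not show that a shift of any given size will occur.

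**The case against.** The strongest case on the other side is one of proportion. This is a haemostasis study sized for feasibility. Its primary outcome already has a masked evaluator, pain is the last of five secondary outcomes, and no pain hypothesis is stated. Both staplers are FDA-approved, and the documents give no reason why a patient would expect one to hurt more. The protocol says staff complete the relevant sections; it does not say that the person questioning the patient has the operative section in hand. Much of this stands: the size and direction of any bias are unknown, and the 60 scores are exposed to bias, not shown to be biased. It does not remove the gap, because nothing in the plan keeps the recorder from seeing the brand and the form as designed displays it.

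A reader might infer several stronger points that the documents do not support:

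- **Each hospital uses its own pain protocol, so scores cannot be pooled.** The text refers only to a standard protocol, and the mention of institutional standard of care concerns the sleeve gastrectomy procedure. What can be said is that the scale and its consistency across three hospitals are undefined. Even with different scales, a stratified or standardised analysis could combine sites, since each surgeon must do at least 5 cases with each brand.
- **There is no analgesic record.** A free-text medications line exists. What is absent is a dedicated, dated postoperative field.
- **Subjects know the brand.** The open-label entry in the Summary concerns investigators. The protocol is silent on subjects, and the consent pages are not part of the text reviewed.
- **Masking would remove the bias.** Staff with chart access, or who attended the case, may still know the brand, and the date-based case identifier makes look-up easy. Masking also does not define a scale or record analgesic use.
- **Nausea and dysphagia outcomes are compromised too.** They are collected on the form but are not listed outcomes.

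**Conclusion.** The point holds as a cheap improvement to a secondary outcome. Following the plan as written, one-week pain is recorded by staff not required to be masked, on a sheet that identifies the stapler, and nothing states that subjects are kept unaware of it. The comparison is open to reporting and recording bias whose size the documents cannot establish. Under the assumed SD of 2 points with 30 per arm, a shift of 0.5 to 1 point would be about 1 to 2 standard errors, enough to raise a nominal 5% false-positive rate to between 16.2% and 49.1%. Both the SD and the shift are assumptions. The primary bleeding endpoint, rated from photographs by a masked evaluator, is outside this point.

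**What to change.** 1. State in the protocol that subjects are not told the assigned stapler until the one-month visit is complete, unless their care requires it.
2. Split Appendix A into an operative page (stapler, reloads, intraoperative items) and a follow-up page that carries only the case identifier.
3. Have the one-week page completed, where possible, by an existing team member who did not attend the case and does not have the operative page. Unmasked staff may still judge whether an adverse event at one month is device-related.
4. Name one pain scale and use it at all three hospitals.
5. Optionally, add a line to the one-week page for postoperative analgesic taken. This is a record only and leaves analgesic care unchanged.

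The cost is a form redesign and a few protocol sentences, with no added visits or procedures. It should need no extra staff, though the documents do not show that every site has an uninvolved team member, hence the qualifier in item 3. The downsides are separate filing of the two pages and masking that remains incomplete.

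### The plan does not place the random assignment after consent and confirmed eligibility, does not conceal it from the open-label surgeons, and makes enrolment depend on stapler use, which comes after assignment.

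*Combined protocol and SAP*

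**What the plan says.** Entry to the study is described in one paragraph under Study Details. It says: "Patients will be screened based on the inclusion and exclusion criteria below and will be consecutively evaluated for study enrollment". It then says: "Each case will be randomly assigned to one of the two FDA approved endoscopic staplers". Next comes the enrolment rule: "Enrollment will be contingent on meeting these criteria, and the use of either the AEON™ Endostapler or the Echelon Flex™ Powered Stapler system from Ethicon". The paragraph closes by defining the span of participation: "Study participation will begin once the subject signs the consent form", ending at the one-month visit.

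Four other places bear on the point:

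- Selection of Subjects lists study consent as an inclusion criterion: "Informed consent for study obtained and signed from each subject". It gives no timing relative to assignment. Use of buttress material is an exclusion criterion.
- Steps and Procedures calls for 60 consecutive cases, 30 per stapler, with at least 5 per stapler for each of three surgeons.
- The Summary states that investigators are not masked and that the primary outcome evaluator is masked to surgeon and device. The title page lists surgeons as principal investigator and co-investigators.
- Withdrawal of Subjects has withdrawn subjects replaced until 60 complete.

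No section says who generates or holds the allocation sequence, how it is concealed, or when the surgeon learns the stapler. None asks for a record of patients screened but not enrolled.

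**The concern.** Randomisation makes the arms comparable only if the decision to enter a patient is made without knowledge of the next assignment. Here the people who consent, schedule and operate are unmasked, and the text does not keep the assignment from them until entry is settled. If a patient thought likely to bleed is deferred or not approached when a particular stapler is next, the arms differ before the first firing. Masked scoring of photographs protects the measurement of bleeding, not the make-up of the arms.

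The enrolment rule adds a second route. It depends on something that happens after assignment, so a patient can be randomised and then, read literally, never become enrolled. With 30 per arm, a few such cases matter.

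Later analysis offers only a partial repair. Appendix A collects age, gender, BMI and medications, so imbalance on those can be examined. Unrecorded factors cannot be, and patients never enrolled leave no trace.

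**Working it through.** **1. What the text fixes and what it leaves open.**

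| Question | Answer in the protocol |
|---|---|
| Is assignment random? | Yes (Study Details) |
| What ratio? | 30:30 (Steps and Procedures) |
| Is study consent required? | Yes, as an inclusion criterion, with no timing against assignment |
| Is assignment made after consent and confirmed eligibility? | Not stated |
| Is it concealed from the surgeons until then? | Not stated |
| Are the surgeons masked? | No (Summary) |
| When does a patient count as enrolled? | When the criteria are met and a study stapler is used (Study Details) |
| Is there a log of patients screened but not enrolled? | Not stated |

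The enrolment row is more than missing detail. It is a stated rule that makes inclusion depend on an event after assignment.

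**2. Illustrative size.** The Statistics section gives no event rate, effect or power calculation, so there is no figure of the plan's to reproduce. All inputs below are assumptions:

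- h, the share of patients recognisably at higher risk: 0.30 to 0.50
- r_H, their bleeding risk: 0.50 to 0.60
- r_L, the risk in the others: 0.20 to 0.30
- s, the share of higher-risk patients kept out of one arm: 0.25 to 0.50
- no true difference between staplers

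In the affected arm the higher-risk share becomes h′ = h(1 − s)/(1 − hs). The spurious difference is

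D = (h − h′)(r_H − r_L) = [hs(1 − h)/(1 − hs)] × (r_H − r_L).

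Over these ranges D rises with h, with s and with the risk gap, so the extremes lie at the corners.

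- Smallest: h = 0.30, s = 0.25, risks 0.50 and 0.30. (0.30 × 0.25 × 0.70)/(1 − 0.075) = 0.0525/0.925 = 0.0568. Multiplied by 0.20, D = 0.0114, or 1.1 points (36.0% against 34.9%).
- Largest: h = 0.50, s = 0.50, risks 0.60 and 0.20. (0.50 × 0.50 × 0.50)/(1 − 0.25) = 0.125/0.75 = 0.1667. Multiplied by 0.40, D = 0.0667, or 6.7 points (40.0% against 33.3%).

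**3. Effect on a test.** The plan names no test. As an illustration, take a two-sided 0.05 chi-square test of any bleeding at 30 per arm, enumerated exactly over the binomial outcomes. The false-positive rate is about 0.05 at the small end and about 0.08 at the large end. With no selection it is about 0.05.

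**4. What follows from the 30:30 count alone.** Suppose the list is a single unblocked 30:30 sequence and someone who knows the running count always guesses the under-filled arm. The expected number of correct guesses is m + (2^(2m)/C(2m, m) − 1)/2. With m = 30 this is 34.4 of 60, or 57%. This holds even for a well-concealed list, so it is a separate and lesser matter. If the assignment itself is visible before consent, no guessing is needed.

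**The case against.** The best answer is that the paragraph already implies the usual order. Screening against the criteria comes before assignment in the text, and signed study consent is one of those criteria. On that reading consent and eligibility come first. The closing sentence on participation defines its start and end and is not a step after assignment. Cases must also be consecutive, so passing over an eligible patient would depart from the protocol.

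Most of this stands. It would be wrong to say that the text places consent after assignment, or that it permits skipping. But sentence order suggests a sequence without fixing it, and it says nothing about concealment. The consecutive rule cannot be checked without a log of those screened and not enrolled.

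A reader might infer that the enrolment rule selects patients by brand. It does not. The condition is met by either study stapler, and its likely purpose is to exclude cases done with a third device. What remains is that it acts after assignment.

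A reader might also infer that the arms will in fact be unbalanced. The documents show only that selection is possible.

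Finally, the 57% guessing rate is weak support. It assumes knowledge of the running count across three surgeons and three hospitals, and sealed envelopes holding a fixed 30:30 list would not change it.

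**Conclusion.** The concern holds in this form: the timing of assignment relative to consent and confirmed eligibility is not specified, its concealment from unmasked surgeon-investigators is not specified, and the enrolment rule rests on an event after assignment, so a randomised patient can go uncounted. Neither the consecutive-case wording nor the masked evaluator closes the gap.

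The range of 1.1 to 6.7 points rests wholly on assumed risks and assumed selection. It shows what such selection could do and is not an estimate of what will happen. The change is worth making because the bias is cheap to prevent and largely beyond repair once patients have been missed.

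**What to change.** Replace the assignment and enrolment sentences under Study Details with wording such as:

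> After signed study consent and confirmation of all preoperative criteria, the research coordinator logs the subject. The stapler assignment is then opened from a concealed sequence (sequentially numbered opaque sealed envelopes or a central list) prepared and held by someone other than the operating surgeons. A subject is enrolled when the assignment is opened, and is counted and analysed in the assigned arm whatever stapler is used.

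Delete the condition that makes enrolment depend on stapler use. Keep a log of every patient screened but not enrolled, with the date and reason.

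Two neighbouring rules should be made consistent with this. The buttress exclusion can be settled during the operation, so the text should say how a case is counted if that happens after assignment. The rule replacing withdrawn subjects should not remove a randomised subject from the count.

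The cost is protocol wording, 60 envelopes or a central list, and a short log kept by the existing coordinator. The sample size does not change. The small downside is that both staplers must be available for each case.

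### Replacement continues until 60 subjects complete one month, although the primary outcome is photographed in surgery, so subjects can be substituted after stapler and bleeding are known

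*Combined protocol and SAP*

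**What the plan says.** Withdrawal of Subjects sets the rule: "Withdrawn subjects will be replaced, until 60 subjects complete the study". Study Details fixes what completion means: "Study participation will begin once the subject signs the consent form and will end after the one-month postoperative follow up visit". Apart from a subject's own choice, withdrawal may be decided by the principal investigator in consultation with the sponsor, for an adverse event, a protocol violation or loss to follow-up. The data of withdrawn subjects are to be collected, but their use in the analysis is not stated.

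Steps and Procedures gives the size: "The study will include 60 total consecutive cases, randomized for stapler type: 30 with the AEON™ Endostapler and 30 with Echelon Flex™", "with at least 5 surgeries of each stapler brand per surgeon". The Summary also puts enrolment at 60, lists the investigators as unmasked and the outcome evaluator as masked to surgeon and device. On allocation, Study Details says: "Each case will be randomly assigned to one of the two FDA approved endoscopic staplers". No sequence generation, concealment or rule for allocating replacements is described.

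The primary outcome is intraoperative staple line bleeding. After the last firing the team is to "count 10 seconds and then capture an image with the laparoscope". A further image is taken earlier if bleeding has to be controlled before then.

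**The concern.** The milestone that triggers replacement is the one-month visit, whereas the primary outcome is complete when the patient leaves theatre. A subject who is stapled and photographed, and then withdrawn in week three, is replaced even though nothing is missing from the primary comparison.

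By the time of such a withdrawal, the unmasked investigators know which stapler was used and have seen how much the staple line bled. Two of the listed reasons, adverse event and protocol violation, involve judgement and could be related to bleeding. The Statistics section leaves the analysis methods to the Clinical Study Report, and no analysis set is defined, so nothing rules out that the 60 completers become the analysis population. Withdrawal followed by replacement would then exchange one known outcome for another. The masked evaluator protects the scoring of images but has no influence on whose images are counted.

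The rule also disturbs the stated totals, and the protocol does not say which of them gives way.

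**Working it through.** **Plan's own figure.** There is no calculation to reproduce. The Statistics section says the number was chosen on feasibility; 30 + 30 = 60 is consistent only as a sum.

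**Timeline.** The order is: consent, first firing, last firing, image 10 seconds later, one-week visit, one-month visit.
- Withdrawal between consent and the first firing: no primary outcome exists, and a replacement supplies one.
- Withdrawal after the image: the primary outcome exists, and a replacement adds a further subject without filling any gap in it.

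The replacement rule treats the two alike.

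**Totals.** With w withdrawals after stapling, 60 completers require 60 + w stapled cases. For w = 1 that is 61, which is neither 60 cases in total nor 30 + 30. Either the 30 and 30 refer to completers, or at least one arm passes 30. Enrolment can remain consecutive beyond 60, but the 60 completers are then a subset with gaps.

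**Enrolment needed.** The documents give no dropout rate, so a range is assumed. N = 60 / (1 − d), rounded up.

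| Assumed d | 60 / (1 − d) | Enrolled | Replacements |
|---|---|---|---|
| 5% | 63.2 | 64 | 4 |
| 10% | 66.7 | 67 | 7 |
| 15% | 70.6 | 71 | 11 |

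**Forced slots, only if 30 and 30 means completers.** Replacements per arm must then equal withdrawals per arm. Assume that the w withdrawals fall at random over two arms of 30 and that the vacancies are filled in random order. A slot is forced when all vacancies still open are in one arm. For j open vacancies this has probability 1 if j = 1 and 2·C(30, j)/C(60, j) if j ≥ 2, which gives 0.4915, 0.2373, 0.1124, 0.0522 and 0.0237 for j = 2 to 6. The expected number of forced slots is the sum from j = 1 to w.

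| w | Expected forced slots | Share of replacements | Chance that all are forced |
|---|---|---|---|
| 1 | 1.00 | 100% | 100% |
| 2 | 1 + 0.4915 = 1.49 | 75% | 49% |
| 3 | 1.49 + 0.2373 = 1.73 | 58% | 24% |
| 4 | 1.73 + 0.1124 = 1.84 | 46% | 11% |
| 6 | 1.84 + 0.0522 + 0.0237 = 1.92 | 32% | 2% |

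A simulation of 40,000 runs agreed to within 0.01, and gave 1.94 for w = 12. The number stays below two.

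**Effect of substitution, only if withdrawn subjects are left out of the analysis.** Suppose k subjects who bled are withdrawn from one arm of 30 and replaced by subjects who bleed at the arm's rate p. The observed rate falls by k(1 − p)/30. For k = 1 and p = 50% that is 0.5/30 = 1.7 percentage points; for k = 3 and p = 20% it is 2.4/30 = 8.0 points. The values of k and p are assumptions for illustration.

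**The case against.** Replacement does serve a purpose. Leakage is followed for one month and device-related adverse events are recorded at that visit, so 60 completers protect the information on those outcomes. Patients are to be evaluated consecutively, which limits anyone's freedom to choose who takes a slot. The evaluator is masked. Withdrawn subjects' data are collected, and nothing says that they leave the primary analysis. These points stand, and they limit the concern to what the rule permits. They do not show that the rule is needed for the primary outcome or that substitution is excluded.

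A reader might go further and infer that every replacement must go to the short arm, that the surgeons can foresee this, and that each replaced subject already had a primary outcome. The documents do not support that:
- The 30 and 30 are attached to randomised cases, and completion to a total of 60. No sentence requires 30 completers per arm, and the statement that each case is randomly assigned can be read to cover replacements.
- Even if 30 per arm does apply to completers, only one or two slots are typically forced, as shown above.
- Open label means that the device in use is known, not that the next assignment is. Foreseeing a forced slot requires the tally of withdrawals by arm across three surgeons and three hospitals, and the protocol does not say who has it. A fixed 30/30 total makes the last assignments predictable even without replacement.
- Participation starts at consent, so some withdrawals precede surgery and leave no image.

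**Conclusion.** The point holds as a weakness in a stated rule that is cheap to remove. Replacement is tied to one-month completion, although the primary outcome is fixed in surgery. For a subject with an image it contributes nothing to that outcome, allows substitution once stapler and bleeding are known, and contradicts the stated total of 60.

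The size depends on assumptions. Non-completion of 5% to 15% means 4 to 11 replacements, and an unknown share of these would be for subjects who already have an image. The shift of 1.7 to 8.0 points in an arm's bleeding rate applies only if withdrawn subjects are excluded and those withdrawn had bled. The forced slots arise only if 30 per arm means completers, and they can be predicted only by someone who knows the tally. Nothing here shows that bias will occur or that the sample size of 60 is wrong.

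**What to change.** Change Withdrawal of Subjects and the matching lines in the Summary and Steps and Procedures as follows:
- Replace only subjects who leave before the first firing. After that no one is replaced, whatever the reason for withdrawal.
- Give each replacement the next concealed random assignment, not the arm of the subject replaced. This presupposes a concealed list, which the protocol should describe.
- Define the target as 60 randomised and stapled subjects.
- Keep every subject with a captured image in the primary analysis by assigned stapler, whether or not they withdraw later. Report a stapled subject without a usable image as missing the primary outcome in the assigned arm.
- Accept a small departure from 30/30, such as 31/29, subject to the minimum of 5 cases per stapler for each surgeon. That minimum accounts for 3 × 5 = 15 cases per stapler, so a small imbalance overall leaves room for it; a list stratified by surgeon would help to meet it.

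The cost is a few sentences and usually fewer patients. The one-month outcomes may have slightly fewer than 60 observations, and the arms may differ by a subject or two.
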